### **15.6 Other Safety Test**

SARS-COV-2 testing will be included in data listings only.

## **16. CHANGES TO PROTOCOL-SPECIFIED ANALYSES**

There are no changes to the planned analyses in the protocol.

## 17. REFERENCES

## 18. APPENDICES

### APPENDIX A: PRESENTATION OF DATA AND PROGRAMMING SPECIFICATIONS

#### General

- Specialized text styles, such as bold, italics, borders, shading, and superscripted and subscripted text, will not be used in tables, figures, and data listings (TFLs) unless they add significant value to the TFL.
- Only standard keyboard characters are to be used in tables and data listings.
- Special characters, such as nonprintable control characters and printer- or font-specific characters, will not be used in a TFL.
- Hexadecimal character representations are allowed (e.g.,  $\mu$ ,  $\alpha$ , and  $\beta$ ).
- All footnotes will be left-justified and at the bottom of a page. Footnotes must be used sparingly and add value to the TFL.

#### Tables

- Means and medians will be presented to 1 decimal place more than the raw data. Standard deviations will be presented to 2 decimal places more than the raw data. Minimums and maximums will be reported with the same number of decimal places as the raw data.
- Percentages will be presented to the tenth place.
- For frequency counts of categorical variables, categories whose counts are zero will be displayed for the sake of completeness. For example, if none of the subjects discontinued due to “lost to follow-up,” this reason will be included in the table with a count of 0. Categories with zero counts will not have zero percentages displayed.
- Lower and upper confidence interval (CI) values must be presented to 1 decimal place more than the raw/derived data (i.e., to the same number of decimal places as the mean).
- Percentiles (e.g., 25% and 75%) must be presented to 1 decimal place more than the raw/derived data.
- For all inferential analyses, *P* values will be rounded to 4 decimal places (or at the highest level of precision) with a leading zero (0.0001). *P* values less than 0.0001 will be presented as “<0.0001.”
- The last footnotes will be:
  - “Source: xxx”, where xxx indicates the source table number(s), if applicable (in case aggregated results, such as the mean or median, are plotted), source listing(s) (in case individual responses are plotted), and source dataset(s) (e.g., analysis data model [ADaM]).
  - “PROGRAM SOURCE: ...\\xx.sas, DATA CUTOFF DATE: DD Mmm YYYY, RUN DATE: DD Mmm YYYY hh:mm”.

## Figures

- Legends will be used for all figures with more than 1 variable or item displayed. Treatment group sizes (n=xx) will be included, as appropriate.
- Figures will be in black and white but can be in color to add value to the clarity and readability of a figure. Lines must be wide enough to see the line after being copied.
- The last footnotes will be:
  - “Source: xxx”, where xxx indicates the source listing number(s) and/or source dataset(s) (eg, ADaM).
  - “PROGRAM SOURCE: ...\\xx.sas, DATA CUTOFF DATE: DD Mmm YYYY, RUN DATE: DD Mmm YYYY hh:mm”.
- Scatter plots will include the regression line. Add text that if a regression line is included. The figure may contain the estimates of the regression model parameters (e.g.,  $y = a + b*x$ ).
- Line graphs over time of change from baseline results will include a horizontal dashed reference line at zero.
- For box plots, the horizontal line will represent the median, “+” will represent the group mean, the length of the box will represent the interquartile range (25th-75th percentiles), and the whiskers will represent the minimum and maximum.

## Listings

- If not otherwise specified, all data listings will be sorted by sequence/treatment, center, subject number, visit, and date/time, as appropriate.
- All date values will be presented in a SAS® statistical software, version 9.4 or higher (SAS Institute Inc) date format (e.g., 29AUG2001).
- All observed time values will be presented using a 24-hour clock format (HH:MM:SS) (e.g., 01:35:45 or 11:26). Seconds will only be reported if they were measured as part of the study.
- The last footnote will be “PROGRAM SOURCE: ...\\xx.sas, DATA CUTOFF DATE: DD Mmm YYYY, RUN DATE: DD Mmm YYYY hh:mm”.

### **Missing or Incomplete Dates (ie, Adverse Events and Concomitant Medications)**

The most conservative approach will be systematically considered. If the adverse event (AE) onset date is missing/incomplete, it is assumed to have occurred during the study treatment phase (i.e., considered a treatment-emergent AE) except if the partial-onset date or other data, such as the stop date, indicates differently. Similarly, a medication with partial start and stop dates could be considered both a prior and concomitant medication.

The following algorithms will be applied to missing and incomplete start and stop dates:

#### Start Dates

- If the day portion of the start date is missing, then the start date will be estimated to be equal to the date of the first dose of study treatment, provided the start month and year are the same as the date of the first dose of study treatment and stop date is either after the date of the first dose of study treatment or completely missing. Otherwise, the missing day portion will be estimated as “01.”
- If both the day and month portions of the start date are missing, then the start date will be estimated to be equal to the date of the first dose of study treatment, provided the start year is the same as the date of the first dose of study treatment and stop date is either after the date of the first dose of study treatment or completely missing. Otherwise, the event will be assumed to start on the first day of the given year (e.g., ??-???-2013 is estimated as 01-JAN-2013).
- If the start date is completely missing and the stop date is either after the first dose of study treatment or completely missing, then the start date will be estimated to be equal to the date of the first dose of study treatment. Otherwise, the start date will be estimated to be the first day of the same year as the stop date. All other non-AE and non-concomitant medication day calculations where only partial dates are available will be handled as follows: the first day of the month will be used in the calculations if the day part of a start date is missing, and 01 January will be used if both the month and day parts of a start date are missing.

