## 8.1 Baseline Values

For this crossover study, 2 types of baseline will be defined as follows:

- The study baseline is defined as the most recent non-missing measurement(s), either scheduled or unscheduled, collected prior to the first dose of study drug in the study. Study baseline may include measurements from Visit 1 (Screening) to Visit 2, prior to the first dose in Treatment Period 1.
- The treatment period baseline is defined as the most recent non-missing measurement(s), either scheduled or unscheduled, collected before the first dose of study drug in each Treatment Period. For Treatment Period 1, baseline may include measurements from Visit 1 (Screening) to Visit 2, prior to the first dose in Treatment Period 1. For Treatment Period 2, the period baseline may include any measurement that occurs after the end of the wash-out period and prior to the first dose at Visit 7 in Treatment Period 2.

Unscheduled visits, repeat measurements, and averages may be used in the determination of baseline values, when applicable.

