### 15.1.2 Adverse Event Analyses

All AE summaries will be restricted to treatment-emergent AEs (TEAEs), defined as those AEs that occurred after the first dose of trial drug or existing AEs that worsened during the study after the first dose administration. If it cannot be determined whether the AE is treatment-emergent because of a partial-onset date, it will be considered treatment-emergent. Verbatim terms in the eCRFs will be mapped to PTs and SOCs using the MedDRA. The version of MedDRA used will be specified in the final Medical Coding Plan.

AEs reported with relationship to study treatment of “Definite,” “Probable,” and “Possible” will be considered related AEs and “Unlikely” and “Not Related” as not related AEs for all relationship-to-study-treatment summaries.

In situations with missing data, the worst-case will be applied; that is, seriousness will be assigned as “Yes” if seriousness is missing, the severity will be assigned as “Severe” if the severity is missing, and relationship to study treatment will be assigned as “Related”.

The following rules will be used to assign a TEAE to a treatment:

- A TEAE will be assigned to the treatment received immediately before onset.

- Any TEAE reported within the washout period between doses will be attributed to the previous treatment received.

Each AE summary will be displayed by treatment group. Summaries displayed by SOC and PT will be ordered by descending order of incidence of SOC and PT within each system organ class. Summaries will display the number and percentage of subjects with at least 1 event by treatment group.

Summaries of the following types will be presented:

- Overall summary of TEAEs that contains an overview of each item below
- Subject incidence of TEAEs and the total number of unique TEAEs by MedDRA SOC and PT.
- Subject incidence and the total number of unique events of Related TEAEs by MedDRA SOC and PT.
- Subject incidence and the total number of unique events of Serious TEAEs by MedDRA SOC and PT
- Subject incidence and the total number of unique events of Serious Related TEAEs by MedDRA SOC and PT
- Subject incidence of TEAEs by MedDRA SOC, PT, and highest severity. At each level of subject summarization, a subject is classified according to the highest severity if the subject reported 1 or more events.

AEs will be listed for all subjects in the Safety population.

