## Standard Calculations

Variables requiring calculation will be derived using the following formulas:

- **Body Mass Index (BMI):** BMI is calculated using height and weight using and is calculated using the following formula:  $BMI (kg/m^2) = weight (kg) / [height (cm) / 100]^2$
- **Change from baseline:** Change from baseline will be calculated using the following formula:  $change = postbaseline\ value - baseline\ value$
- **Percent change from baseline:** Percent change from baseline will be calculated using the following formula:  $percent\ change\ from\ baseline = (postbaseline\ value - baseline\ value) / baseline\ value \times 100$ .
- **Study day:** For a given date, the study day will be calculated as the number of days from the day of first dosing of study treatment, labeled day 1, therefore:

Study day = date of event/measurement - date of first dose of study treatment + 1, for events/measurements on or after first dose

Study day = date of event/measurement - date of first dose of study treatment, for events/measurements before first dose

- **Durations (days):** Durations, expressed in days, will be calculated as follows:

Duration in days = (Stop date/time of event – Start date/time of event)/(3660x24)

If the stop or start time is missing, only the date information will be used as follows:

[figure not shown]
Duration in days = Stop date of event – Start date of event + 1

- **Height:** Height entries made in inches will be converted to centimeters using the following formula:

Height (cm) = Height (in) × 2.54

- **Weight:** Weight entries made in pounds will be converted to kilograms using the following formula:

Weight (kg) = Weight (lb)/2.2046

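### SAP Appendix A imputes incomplete AE start dates without regard to period, so on its most natural reading most incompletely dated Period 2 AEs are counted under the Period 1 treatment (minor, cheap to correct)

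*SAP*

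**What the plan says.** SAP Appendix A (Start Dates) handles three patterns of incomplete AE start date.

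- Day missing: "the start date will be estimated to be equal to the date of the first dose of study treatment, provided the start month" and year agree with that date and the stop date is later or missing. "Otherwise, the missing day portion will be estimated as" 01.
- Day and month missing: the first-dose date if the year agrees and the same stop-date condition holds; if not, 01 January.
- Nothing known: the first-dose date, if the stop date is after it or also missing.

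The paragraph introducing these rules is about treatment emergence. An incompletely dated AE is taken to be treatment-emergent "except if the partial-onset date or other data, such as the stop date, indicates differently".

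SAP 15.1.2 then uses onset for a second purpose: "A TEAE will be assigned to the treatment received immediately before onset". For the gap between periods, "Any TEAE reported within the washout period between doses will be attributed to the previous treatment received". On partial onset dates, 15.1.2 settles only whether the event is treatment-emergent. Neither section says how to find the period, and Appendix A never mentions the Period 2 first dose. Protocol 10.5 defers conventions for missing AE information to the SAP.

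**The concern.** The Appendix A rules suit a parallel-group trial, where emergence is the only question that an onset date must answer. Here the onset date also decides which treatment is charged with the event. A rule that pulls incomplete dates back to the first dose, or to the start of a month or year, pulls Period 2 events back into Period 1 or the washout, and both of those belong to the Period 1 treatment. An AE on ADX-629 in Period 2 could then be tabulated under placebo, or the reverse. TEAE and SAE incidence and severity are primary endpoints (SAP 3.3), so the by-treatment tables should not depend on a date convention built for another purpose.

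**Working it through.** **Readings.** Two points are not spelled out in the SAP.

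1. Which first dose Appendix A means. Under Standard Calculations, "the study day will be calculated as the number of days from the day of first dosing of study treatment, labeled day 1" gives a single Day 1 for the study, and the emergence purpose fits that. SAP 8.1 marks the two levels explicitly ("collected prior to the first dose of study drug in the study" and "collected before the first dose of study drug in each Treatment Period"); the Start Dates text marks neither.
2. Whether onset in 15.1.2 includes an imputed onset. SAP 11.5 says imputed for medications; 15.1.2 does not say it for AEs.

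The main calculation takes the first dose in the study and uses imputed onsets.

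**Inputs.** Dosing 14 (±2) days per period (Protocol 7.1), washout 14 ±2 days (Protocol 5.1), and end-of-trial visit about 14 days after the last dose (Protocol 5.1). Assumptions: first-dose dates uniform over a 365-day year, onsets uniform over the window, and stop date after the first dose or missing. An AE is moved if its imputed date falls before the Period 2 first dose.

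**Example.** First dose 12 Sep 2022, Period 2 first dose 10 Oct, AE on 17 Oct. With the day missing, the imputed date is 01 Oct, in the washout, so the Period 1 treatment is charged. With day and month missing, or nothing known, it is 12 Sep, in Period 1.

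**Day missing.** An AE moves when its onset month is also the month of the Period 2 first dose, unless that dose falls on the 1st. With n onset days and a mean month of 365/12 = 30.42 days, the share is 1 − [(n−1)/2]/30.42 − 12/365:

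- n = 14 dosing days: 1 − 6.5/30.42 − 0.033 = 75.3%
- n = 12 and n = 16 dosing days: 78.6% and 72.1%
- n = 28 (14 dosing plus 14 follow-up days): 1 − 13.5/30.42 − 0.033 = 52.3%

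For a given n, the length of the washout does not change the share. Almost all of these moves come from the day-01 clause. Only about 1% of day-missing AEs in Period 2 dosing share a month with the first dose in the study when the periods start 28 days apart.

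**Day and month missing.** An AE escapes only if the year turns during Period 2 before onset, or if Period 2 starts on 01 January: [(n−1)/2 + 1]/365. For n = 14 that is 7.5/365 = 2.1%, so 97.9% move. For n = 28 it is 14.5/365 = 4.0%, so 96.0% move.

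**Nothing known.** 100% move.

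**Reverse moves** (Period 1 or washout AE sent to Period 2): 0 in a full enumeration of dates, which also reproduces the shares above.

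**Alternative reading.** Suppose Appendix A meant the Period 2 first dose whenever the month matches. Then no day-missing Period 2 AE moves, but some from Period 1 dosing could move forward if the stop date is later or missing. The upper bounds are 39.2% (12 dosing and 12 washout days), 29.3% (14 and 14) and 19.9% (16 and 16).

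**Effect on the reported unit, subjects with at least one TEAE.** Assume 25 subjects per sequence, incidences of 30% (ADX-629) and 15% (placebo), and Poisson events. The rates are La = −ln(0.70) = 0.357 and Lb = −ln(0.85) = 0.163. Let q = (share of AEs incompletely dated) × (share of those moved). Then

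- ADX-629 = 25[1 − exp(−(La + q·Lb))] + 25[1 − exp(−La(1−q))]
- placebo = the same with La and Lb exchanged

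With q = 0 the difference is 15.0 − 7.5 = 7.5 subjects.

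| Incomplete × moved | q | Difference | Loss |
|---|---|---|---|
| 2% × 52.3% | 0.0105 | 7.42 | 0.08 |
| 2% × 75.3% | 0.0151 | 7.39 | 0.11 |
| 5% × 52.3% | 0.0262 | 7.30 | 0.20 |
| 5% × 75.3% | 0.0377 | 7.22 | 0.28 |
| 5% × 100% | 0.0500 | 7.12 | 0.38 |

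Period 2 contains 25(0.357 + 0.163) = 12.98 expected events, so between 0.14 and 0.65 of an event moves. For incidences from 20% vs 10% to 40% vs 20%, the loss runs from 0.05 to 0.50 of a subject.

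**The case against.** The strongest objection is materiality. The loss is below half a subject under the main assumptions. TEAEs are summarized descriptively (Protocol 10.5), no test depends on them, and every AE is listed. Dates are to be recorded as precisely as possible (Protocol 8.3.1.2), missing information is queried (9.3), and a pre-lock review settles data issues (10.1.3). All of this stands and is why the point is minor. These safeguards make incomplete dates rarer, but they supply no rule for those that remain.

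Second, the direction depends on the two readings above. That is also true. But the other readings do not close the gap. If the period's own first dose is meant, the rule cannot be applied until the period is known. If imputed onsets are not used, 15.1.2 has no onset to work with.

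Third, the exception for other data could be said to let the stop date or other information override the default. As written it does so only for treatment emergence, not for period.

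A reader might infer something stronger: that the rule favors ADX-629 or hides a safety signal. The documents do not support that. With balanced sequences, ADX-629 events moved to placebo in one sequence are mirrored by placebo events moved to ADX-629 in the other, so the difference shrinks slightly and neither treatment gains. The overall number of TEAEs does not change, nor do the laboratory, vital sign and ECG results.

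**Conclusion.** The gap is real and minor. Followed as written, with the first dose taken as the first in the study and imputed onsets used, Appendix A and 15.1.2 together put most incompletely dated Period 2 AEs under the Period 1 treatment: about 75% with only the day missing and onset during 14 dosing days (72-79% for 16 to 12 days), 52% when 14 days of follow-up are included, 96-98% with day and month missing, and 100% with nothing known. These shares rest on uniform dates.

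The consequence is a slight dilution of a descriptive comparison. With assumed incidences of 30% vs 15% and an assumed 2-5% incomplete dates, the loss is about 0.1-0.3 of a subject if only the day is missing. The upper figure of 0.4 requires every incomplete date to be fully missing. The documents give neither the incidences nor the rate of incomplete dates. The reason to act is that a primary endpoint is involved and the correction is cheap, not that conclusions are likely to change.

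**What to change.** In SAP 15.1.2 and Appendix A:

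1. First place an incompletely dated AE in a period, using the known month and year, the stop date and, if the eCRF holds it, the visit of first report. AEs are recorded before dosing at Visit 7 and again at Visits 8 to 10 (Protocol 5.2.2.4 to 5.2.2.7), so one first reported at Visit 8 or later can normally be placed in Period 2. Protocol 8.3.1.2 does not list the visit of report among the AE page items, so check the annotated eCRF before relying on it.
2. When only Period 2 is possible, impute no earlier than the Period 2 first dose. Where the period can be identified, this removes the misassignment.
3. State that *first dose of study treatment* means the first in the study, and that 15.1.2 uses the imputed onset.
4. For AEs whose period stays ambiguous, fix the assignment rule before unblinding, footnote their number, and show the by-treatment TEAE summary with them assigned each way. Counting them under both treatments is possible, but it inflates both arms and also dilutes the difference.

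The cost is a few sentences, a small programming change and possibly one extra descriptive table. AEs mentioned later than the visit at which they should have been reported can still be misplaced.

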#### Stop Dates

- If only the day of resolution is unknown, the day of resolution of the event will be assumed to be the last day of the month (e.g., ??-JAN-2013 will be treated as 31-JAN-2013).
- If both the day and month of resolution are unknown, the day of resolution of the event will be assumed to be the last day of the year (e.g., ??-???-2013 will be treated as 31-DEC-2013).
- If the stop date of the event is completely missing or the event is continuing, the event resolution will be assumed to be after the first dose of study treatment, and the stop date will be imputed using the last known date on the study.

## Standard Calculations

Variables requiring calculation will be derived using the following formulas:

- **Body Mass Index (BMI):** BMI is calculated using height and weight using and is calculated using the following formula:  $BMI (kg/m^2) = weight (kg) / [height (cm) / 100]^2$
- **Change from baseline:** Change from baseline will be calculated using the following formula:  $change = postbaseline\ value - baseline\ value$
- **Percent change from baseline:** Percent change from baseline will be calculated using the following formula:  $percent\ change\ from\ baseline = (postbaseline\ value - baseline\ value) / baseline\ value \times 100$ .
- **Study day:** For a given date, the study day will be calculated as the number of days from the day of first dosing of study treatment, labeled day 1, therefore:

Study day = date of event/measurement - date of first dose of study treatment + 1, for events/measurements on or after first dose

Study day = date of event/measurement - date of first dose of study treatment, for events/measurements before first dose

- **Durations (days):** Durations, expressed in days, will be calculated as follows:

Duration in days = (Stop date/time of event – Start date/time of event)/(3660x24)

If the stop or start time is missing, only the date information will be used as follows:

[figure not shown]
Duration in days = Stop date of event – Start date of event + 1

- **Height:** Height entries made in inches will be converted to centimeters using the following formula:

Height (cm) = Height (in) × 2.54

- **Weight:** Weight entries made in pounds will be converted to kilograms using the following formula:

Weight (kg) = Weight (lb)/2.2046

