### Before Dosing:

- Review inclusion and exclusion criteria (Visit 3 only).
- Collect vital signs (blood pressure, heart rate, respiratory rate, temperature, and oxygen saturation).
- Record changes in concomitant medications.
- Symptomatic physical examination may be performed, if deemed necessary (e.g., to record any changes since screening or due to an AE). This may require an additional visit to the investigative site.

CONFIDENTIAL Page 32 of 68

- Record standard 12-lead ECG.
- Collect blood sample for routine laboratory testing (biochemistry and hematology).
- Collect urine sample for urinalysis and urine/creatinine ratio.
- Perform urine pregnancy test (women of childbearing potential).
- Perform urine drug screen.
- Perform SARS-CoV-2 test (Day 1 of Treatment Period 2 only).
- Record cough severity VAS.
- Complete LCQ.
- Complete CQLQ.
- Record any AEs since the last visit.
- The cough recorder will be disconnected 24 hours after fitting and retained by the investigative site.
- The first dose of trial treatment will be dispensed, and subjects will take the first dose (this must be after the completion of the cough monitoring).
- Visit 7 only: Unused trial medication and empty containers from Treatment Period 1 will be returned.

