## After Dosing:

- Collect vital signs (blood pressure, heart rate, respiratory rate, temperature, oxygen saturation) and record 2 hours (±30 minutes) after dosing.
- Dispense trial treatment to take home.

The subject will take the second dose of trial treatment at home before bedtime and will continue to take the randomized treatment twice daily for 14 days.

#### 5.2.2.5 Treatment Period Procedures - Visits 4 and 8

This visit may be conducted at the clinic or at another location such as the subject's home, according to the preference of the subject.

The following assessments and procedures will be performed:

- Collect vital signs (blood pressure, heart rate, respiratory rate, temperature, and oxygen saturation).
- Record changes in concomitant medications.
- Symptomatic physical examination may be performed, if deemed necessary (e.g., to record any changes since screening or due to an AE). This may require an additional visit to the investigative site.
- Record any AEs since the last visit.

CONFIDENTIAL Page 33 of 68

Subjects should be fitted with a cough recorder by 10:00 am. The cough recorder must be worn for 24 hours between fitting and disconnection. The subject will take the trial treatment at home before bedtime and will continue to take the randomized treatment twice daily.

## 5.2.2.6 Treatment Period Procedures - Visits 5 and 9

The following assessments and procedures will be performed:

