7.4 Selection of Doses and Timing of Dose for Each Subject

## 7.5 Packaging and Labeling

The Sponsor will be responsible for ensuring that ADX-629 and placebo tablets are manufactured in accordance with applicable current Good Manufacturing Practice regulations and requirements.

CONFIDENTIAL Page 42 of 68

ADX-629 tablets or placebo will be provided in treatment kits for each period between trial visits. Each of the product bottles is capped with a child-resistant closure liner with an induction seal.

The IP will be administered as 300 mg tablets, i.e., one tablet BID for 14 days. BID dosing means every  $12 (\pm 1)$  hours. Each container will hold sufficient tablets to cover the time until the next scheduled visit, plus overage in case the scheduled visit is delayed.

The IP will be labeled according to the requirements of local law and legislation.

Further details regarding packaging, labeling and accountability are provided in the pharmacy manual.

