### 14. EXTENT OF EXPOSURE

Study treatment exposure will be summarized for each treatment group using the total number of doses taken and the duration of treatment.

Duration of study treatment will be calculated as follows:

- Duration of study treatment administration (days) = date/time of last administration – date/time of first administration

Study treatment compliance will be calculated as follows:

- Compliance (%): (actual number of used tablets in total) / (number of prescribed tablets to be taken) × 100
- Actual number of used tablets: number of tablets dispensed – number of tablets returned
- Prescribed number of tablets to be taken: duration of study treatment administration (days) × number of daily tablets

Study treatment compliance will be summarized by treatment group using counts and percentages as categorized below:

- >100%
- >90% to 100%
- >80% to 90%
- >70% to 80%
- ≤70%

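### SAP Appendix A converts date/time differences to days with 3660×24 instead of 3600×24, so durations derived that way are 1.64% short (minor)

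*SAP*

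**What the plan says.** SAP Appendix A, Standard Calculations, lists the formulas from which variables will be derived. Where both clock times are known, the rule is "Duration in days = (Stop date/time of event – Start date/time of event)/(3660x24"). Where a time is missing, only dates are used: "Duration in days = Stop date of event – Start date of event + 1".

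SAP Section 14 (Extent of Exposure) defines "Duration of study treatment administration (days) = date/time of last administration – date/time of first administration". It shows no divisor and does not refer to Appendix A. The same duration sets the compliance denominator: "Prescribed number of tablets to be taken: duration of study treatment administration (days) × number of daily tablets". The numerator is "Actual number of used tablets: number of tablets dispensed – number of tablets returned". Compliance is then tabulated in five classes, with cuts at 100%, 90%, 80% and 70%.

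On dosing, Protocol Section 7.5 states "The IP will be administered as 300 mg tablets, i.e., one tablet BID for 14 days". On Day 1, "subjects will take the first dose (this must be after the completion of the cough monitoring"), and then "The subject will take the second dose of trial treatment at home before bedtime" (Protocol Section 5.2.2.4). The last dose of a period is taken on the evening of Day 14 (Protocol Section 5.2.2.6).

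**The concern.** The divisor 3660×24 is not the length of a day in any unit. A day is 86,400 seconds, 1,440 minutes or 24 hours. The evident intention is 3600×24.

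This is an operative formula in the programming specification. A programmer who follows it gets durations that are too short. One who silently uses 3600 departs from the plan, and SAP Section 1 requires deviations to be documented in the study report. Independent programming against the same text would reproduce the constant rather than catch it.

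The outputs at stake are exposure duration and the compliance percentages built on it. A denominator that is too small makes compliance look slightly better than it was.

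**Working it through.** **Inputs**
- Divisor: 3660×24 (SAP Appendix A, Standard Calculations).
- Duration: first to last administration (SAP Section 14).
- Prescribed tablets: duration × 2 (SAP Section 14; two tablets a day from Protocol Section 7.5).
- Tablets per period: 2 × 14 = 28.
- Timing: first dose on Day 1 after the recorder comes off, last dose on the evening of Day 14 (Protocol Sections 5.2.2.4 and 5.2.2.6).
- Assumptions: Section 14 uses the Appendix A conversion; date/times differ in seconds; the Day 1 dose is a morning dose; doses are 12 hours apart; missed tablets fall between the first and last dose.

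**Step 1: the constant.** 3660 × 24 = 87,840, and 60 × 60 × 24 = 86,400. The ratio is 86,400 / 87,840 = 0.9836, so durations are 1.64% short. Anything divided by such a duration is too large by 87,840 / 86,400 = 1.0167. These proportions do not depend on the length of the course.

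**Step 2: exposure.** Twenty-eight doses span 27 intervals of 12 hours: 27 × 12 / 24 = 13.5 days = 1,166,400 seconds.
- Correct divisor: 1,166,400 / 86,400 = 13.50 days, so 27.00 prescribed tablets.
- Printed divisor: 1,166,400 / 87,840 = 13.28 days, so 26.56 prescribed tablets.

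**Step 3: compliance** = tablets used / prescribed × 100.

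| Tablets used | With 3600×24 | Class | With 3660×24 | Class | Change |
|---|---|---|---|---|---|
| 28 | 103.7% | >100% | 105.4% | >100% | no |
| 27 | 100.0% | >90% to 100% | 101.7% | >100% | yes |
| 26 | 96.3% | >90% to 100% | 97.9% | >90% to 100% | no |
| 25 | 92.6% | >90% to 100% | 94.1% | >90% to 100% | no |
| 24 | 88.9% | >80% to 90% | 90.4% | >90% to 100% | yes |

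From 23 down to 18 tablets, no class changes.

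**Step 4: other spans.** The counts that cross a cut depend on the span. I take 13.33 to 13.58 days as an assumed range.
- At 13.58 days (27.16 tablets), 27 used still crosses: 27 / 27.16 = 99.4%, × 1.0167 = 101.1%. But 24 used no longer does: 88.4% becomes 89.8%.
- At 13.33 days (26.66 tablets), 27 used is above 100% under either divisor: 27 / 26.66 = 101.3%. Here 21 used crosses the 80% cut: 78.8% becomes 80.1%.
- A fully compliant subject is above 100% throughout: 105.0% to 103.1% with the correct divisor, 106.8% to 104.8% with the printed one.

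**Step 5: date/time against date-only.** The fallback gives 14 − 1 + 1 = 14 days for the same course, and 14 × 2 = 28 prescribed tablets. The gap from 13.28 is 0.72 day. Of this, 14 − 13.5 = 0.50 day comes from the added day and 13.5 − 13.28 = 0.22 day from the divisor.

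**The case against.** A reader might infer that the divisor is what pushes a fully compliant subject into the class above 100%. The documents do not support that. Under Section 14 as written, 28 doses span 27 intervals, so full compliance is 28/27 = 103.7% with the correct constant. Only a span of exactly 14.0 days would go from 100.0% to 101.7%, and the dosing schedule does not produce that span. If the prescribed count were simply set to 28, compliance would be 28/28 = 100% and no divisor would enter.

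A second tempting reading is that durations throughout the report are wrong. Section 14 is the only use I can identify in the readable text:
- SAP Section 11.5 rules out durations from imputed medication dates.
- The adverse event summaries in SAP Section 15.1.2 contain none.
- Years of cough come from ages (SAP Section 11.4.1).

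The table index in Appendix C is not readable, so other uses cannot be excluded.

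Three further objections stand in part. Section 14 never cites Appendix A, whose formula is worded for events, so the link is an inference. The error is also small: 27.00 − 26.56 = 0.44 of a tablet. The limits of <80% and >120% in Protocol Section 7.8 are applied at the site from tablet counts and are not tied to this formula. Finally, the constant appears once in machine-read text, so a misread digit is possible.

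None of this makes 87,840 a day.

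**Conclusion.** The divisor as printed is wrong, and any duration derived with it is 1.64% too short. If Section 14 uses it, which is reasonable because the readable SAP contains no other date/time-to-days conversion, a 13.5-day course is reported as 13.28 days and compliance rises by a factor of 1.017. At that span two tablet counts, 27 and 24 of 28, move up one class. Which counts move depends on the actual span.

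The effect is limited to descriptive exposure and compliance output. No efficacy test uses the formula. The figure above 100% for a fully compliant subject is a separate defect of Section 14, and correcting the divisor only lowers it from 105.4% to 103.7%. Severity: minor.

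**What to change.** Check the digit against the source page. If it is printed as read, replace (3660x24) with (3600x24) in the Durations entry of Appendix A and in any program that copied it. The cost is one constant, with no downside.

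State in Section 14 which Appendix A rule it uses, so that the conversion no longer has to be inferred.

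Separately, correct Section 14 so that 28 of 28 tablets gives 100%. One way is to take last dose date minus first dose date plus 1, which gives 14 days and 28 prescribed tablets. Changing the constant alone will not achieve this.
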